7.6.6. Handling of missing data

For management of missing data in the primary analysis, i.e., missing daily reports, the number of migraine days per each 28-day period in the Treatment phase will be prorated (normalized) to a 28-day. For example, if a patient had 24 reported days during weeks 9-12, with 7 migraine days, her number of migraine days in this period will be normalized to $(7/24) * 28 = 8.17$

7.6.7. Interim analysis

One interim analysis is planned after at least 35% of the data is collected (~84 participants in both arms [42 per arm]). The study will continue to the originally planned sample size if the results are favorable (difference between groups in the mean reduction of migraine days of at least 1 migraine day). The interim analysis will be performed on both the mITT and ITT analysis sets, and the enrollment may be stopped due to futility if the interim effects fall below the threshold.

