7.4. Sample size

A sample size of 234 participants, 117 per each treatment arm, was determined to provide 80% power to detect a mean ($\pm SD$) difference of 2 ± 3.0 in the reduction in number of migraine headache days from the baseline to weeks 9-12 of the treatment phase, between the active group and the sham group at a two-sided alpha level of 0.05. With an anticipated discontinuation rate of about 35%, up to 375 participants are planned to be enrolled. In case of higher dropout or non-eligible participants or missing data, enrollment may be extended in order to reach the desired sample size.

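### The 80% power in section 7.4 leaves out the 1-day futility bar in section 7.6.7; the power should be restated with that rule included, and one analysis set should be named to govern the interim decision

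*Combined protocol and SAP*

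**What the plan says.** Section 7.4 (Sample size): "A sample size of 234 participants, 117 per each treatment arm", "was determined to provide 80% power to detect a mean" "difference of 2 ± 3.0 in the reduction in number of migraine headache days", "between the active group and the sham group at a two-sided alpha level of 0.05". The section does not mention the interim look.

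Section 7.6.7 (Interim analysis) plans one look once at least 35% of the data are in, about 42 per arm. The study continues to full size if the result is favorable, defined as a "difference between groups in the mean reduction of migraine days of at least 1 migraine day". Otherwise "enrollment may be stopped due to futility if the interim effects fall below the threshold". The look is "performed on both the mITT and ITT analysis sets".

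Sections 7.5 and 7.6.3 make mITT the primary set for efficacy. Section 7.6.7.1 has a committee recommend whether to continue, and section 13.1 leaves termination to the sponsor. No section gives a stopping probability, a conditional power or a reason for the 1-day value. No section says what happens if one analysis set falls above 1 day and the other below.

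**The concern.** A futility rule removes some trials that would have ended significant, so the power of the whole design is lower than that of the final test alone. How much lower depends on how far the bar lies below the effect that the trial is planned for, measured in interim standard errors. The plan quotes a fixed-sample power and a stopping bar side by side and never connects them.

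Two things are at stake. First, an effective device could be stopped at about 36% of the data more often than the plan discloses. Second, the committee would receive two estimates with no rule for choosing between them. Futility-only stopping does not inflate the type I error, so there is no added risk of a false efficacy claim.

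**Working it through.** **Inputs.** Difference 2 days, SD 3.0, two-sided alpha 0.05, 80% power and 117 per arm come from section 7.4. The interim size (42 per arm) and the 1-day bar come from section 7.6.7. The independent t-test comes from section 7.2.1.

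**1. The plan's own figure.** n per arm = 2 × (1.96 + 0.8416)² × 3.0² / 2² = 35.3, so 36 rather than 117. At 117 per arm, 2 ± 3.0 has 99.9% power. The stated 80% does not follow from the stated inputs. Holding 117 per arm, 80% power and 2 days fixed and solving for the SD gives 5.44 (noncentral t) or 5.46 (normal approximation). **This SD is an assumption; the documents do not give it.**

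**2. Formulas.** Interim SE = SD × √(2/42). Final SE = SD × √(2/117). Smallest significant final difference = 1.96 × final SE. P(stop) = Φ((1 − 2)/interim SE) for a true difference of 2 days. Power with the bar followed = P(interim difference ≥ 1 and final z > 1.96), bivariate normal with correlation √(42/117) = 0.599.

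**3. Results at a true difference of 2 days**

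| SD | Interim SE | Smallest significant final difference | P(stop) | Power, no bar | Power, bar followed | Loss (points) |
|---|---|---|---|---|---|---|
| 3.0 (stated) | 0.655 | 0.77 | 6.3% | 99.9% | 93.6% | 6.3 |
| 3.5 | 0.764 | 0.90 | 9.5% | 99% | 90% | 9.0 |
| 4.0 | 0.873 | 1.03 | 12.6% | 97% | 86% | 10.7 |
| 5.0 | 1.091 | 1.28 | 18.0% | 86% | 76% | 10.9 |
| 5.44 (assumed) | 1.187 | 1.39 | 20.0% | 80% | 70% | about 10 |
| 6.0 | 1.309 | 1.54 | 22% | 72% | 63% | 9.0 |

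A simulation of 200,000 trials with the t-test agrees: 99.9% to 93.7% at SD 3.0, and 79.7% to 69.9% at SD 5.46.

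**4. The bar against the final threshold.** They are equal where 1.96 × SD × √(2/117) = 1, at SD = 3.90. Below that SD the interim asks for a larger observed difference than the final test needs. Above it, the interim asks for a smaller one.

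**5. Conditional power on the current trend at exactly 1.0 day.** Let t = 42/117 = 0.359 and z = 1/interim SE. Conditional power = Φ((z/√t − 1.96)/√(1 − t)).
- SD 3.0: z = 1.527, z/√t = 2.549, so Φ(0.736) = 77%.
- SD 5.44: z = 0.842, z/√t = 1.406, so Φ(−0.692) = 24%.

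**6. What a lower bar would trade.** With a 0-day bar, power at 2 days is 99.8% (SD 3.0) or 79% (SD 5.44). With no true effect, a 0-day bar stops 50% of trials. The 1-day bar stops Φ(1/0.655) = 94% (SD 3.0) or Φ(1/1.187) = 80% (SD 5.44).

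**The case against.** On the plan's stated inputs the design keeps about 93.6% power with the bar followed to the letter, well above 80%. The 70% figure needs an SD that the plan never states, and it arises only because 117 per arm does not follow from 2 ± 3.0, which is a separate fault in section 7.4. The stopping language is permissive, a committee only recommends, and the sponsor decides. The look comes after at least 35% of the data, and a later look would cost less power. Section 7.6.7.2 also leaves room for a sample-size change. Finally, how much power to give up for early stopping of an ineffective device is a legitimate sponsor choice.

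All of this stands, and it limits the point. It does not remove it. Section 7.6.7 ties continuation to the 1-day difference and offers the committee no other numerical criterion, so the losses above are what the written rule implies if it is used. If the rule is meant as advisory, the plan should say so. Nothing in the objection supplies the missing operating characteristics or settles a disagreement between mITT and ITT.

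Three stronger readings are tempting, and the documents do not support them:

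- *The trial fails to deliver its 80% power.* This is not so at 2 days and SD 3.0. It holds only under an assumption that reconciles 117 per arm with 80%.
- *The bar is over-strict and also costs 10 points of power.* At a 2-day effect these do not combine into one large fault: the bar exceeds the final threshold only below SD 3.90, whereas at SD 5.44 it lies under the 1.39-day threshold and a trial at the bar has only 24% conditional power on trend.
- *Power falls to about 52%, with 44% of trials stopped.* That is the result for a true effect of 1.10 days at SD 3.0, the effect that 117 per arm detects with 80% power. The plan names 2 days as its target and makes no claim for 1.10.

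**Conclusion.** The point holds as a reporting and specification gap; should-fix. The power in section 7.4 ignores the stopping rule in section 7.6.7.

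- **Stated inputs (2 days, SD 3.0):** 99.9% without the bar and about 93.6% with it. The target is met, but the bar is higher than the 0.77 day that would be significant at the end, and a trial exactly at the bar still has 77% conditional power on trend.
- **Assumed SD of about 5.44 (117 per arm giving 80% for 2 days):** a 20% chance of stopping and about 70% power. Here the issue is the undisclosed loss, not an over-strict bar.
- **In between:** the loss is about 9 to 11 points for SD 3.5 to 6.

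These figures assume a look at 42 per arm, a single analysis set and a rule that is followed. Overriding the rule would shrink the loss. Requiring both sets to clear the bar can only raise the chance of stopping. The separate gap, no rule for discordant mITT and ITT results, depends on no assumption about SD.

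**What to change.** 1. In section 7.4, reconcile the difference, SD and power with 117 per arm, then restate power with the futility rule included: about 94% if SD 3.0 is kept, about 70% if the SD is about 5.44.
2. In section 7.6.7, name mITT, already primary for efficacy, as the set that governs the interim decision, with ITT as supporting information.
3. State explicitly that the futility rule is non-binding.
4. Report the bar's operating characteristics at the reconciled SD: the chance of stopping at the design effect and under no effect, and conditional power at the bar.

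The sponsor may also consider a lower bar, set by conditional power at the reconciled SD. The price is fewer early stops if the device does nothing: with a 0-day bar, 50% against 80% to 94% now. The value of the bar therefore remains the sponsor's choice.

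Items 1 to 4 cost only protocol and SAP wording plus a short calculation. They should be in place before the interim look, because a later change could appear driven by the data.

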7.6.7.1. Procedure

After all the relevant data will be entered into the database, a soft lock to the database will be performed. An independent unblinded statistician will perform the assessments described below. A designated decision committee will recommend whether to continue or stop the study once the interim results are available.

In the interim analysis, the data of all evaluable subjects enrolled up to that point will be analyzed.

	QMS document Nerivio TCH-008 Clinical Study Protocol	Doc ID: TEC0250 Revision #: 3.0 Page: 46 of 58
---	--	--

7.6.7.2. Blinding

Only the unblinded statistician and the two other members of the DMC will be exposed to the interim report. This team may also have access to the unmasked information of the interim analysis. The investigators and company directors will only be informed of a decision to continue or to discontinue the trial, or to implement modifications in trial procedure and/or sample size. The unblinded statistician who is responsible for conducting the interim analyses should ensure that the unmasked data is not available to any unauthorized person within or outside the company.

Only the decision and recommendation will be shared with the sponsor and the study personnel.

7.7. Randomization

After a subject meets the eligibility criteria, he/she will be equally allocated (with a 1:1 ratio) to one of the following treatment groups based on a randomization scheme with blocks stratified by center:

- Active
- Sham

Subjects will be stratified according to their headache days frequency reported during the baseline phase, to achieve approximately equal numbers of chronic and non-chronic participants. High frequency (HF) group will contain all subjects reported 15 headache days or more, and low frequency (LF) group will contain all subjects reported less than 15 headache days. The stratified randomization will allow a balance in the number of headache days between treatment groups and prevent bias in the mean change of migraine/headache days.

The randomization scheme will be prepared by a biostatistician using a random number generating procedure.

7.8. Blinding

This is a double-blind study, the subjects, and investigators will be blinded to the treatment allocated to each subject. The study personnel will be blinded to the randomization block size.

Each device will be programmed with one of two versions of firmware that deliver either active or sham electrical stimulation. In all other aspects, the active and the sham conditions will be kept identical.

	QMS document Nerivio TCH-008 Clinical Study Protocol	Doc ID: TEC0250 Revision #: 3.0 Page: 47 of 58
---	--	--

8. DATA MANAGEMENT

8.1. Data capture

Data capture will be performed using an electronic data collection (EDC) system in conjunction with electronic patient reported outcome (PRO) collection tools implemented in the smartphone application. The clinical sites will use electronic case report forms (eCRFs) to document the information required by the study CIP.

The EDC provider is FlaskData.IO. The EDC enables secure collection, transmission, validation, monitoring and real-time administration of the data collected at the sites and by the smartphone application. The system offers a password-restricted access to clinical trial information based on individuals' roles and responsibilities. The EDC is compliant with 21 CFR Part 11 and FDA's "Guidance: Computerized Systems Used in Clinical Investigations."

Except for patient reported outcomes which are directly reported by the participants in the smartphone application, data reported on the eCRF should be driven from source documents and should be consistent with these source documents. Editing of data will be done with a full audit trail.

PRO data collected from the smartphone application will be saved in dedicated log files on the smartphones for backup purposes and transferred to the EDC system.

8.1.1. Direct data entry

For several CRF fields, source data verification (SDV) may not be possible as entries may not be found in source documents (i.e. patient reported outcome completed directly into the smartphone app). Therefore, the CRF may be used for direct data entry, but only in pre-defined fields.

8.2. Data quality assurance

To ensure the quality of clinical data across all subjects, a clinical data management review of the patient data in the CRF will be performed by the sponsor. During this review, patient data will be assessed for consistency, omissions, and any apparent discrepancies. In addition, the data will be reviewed for adherence to the CIP and relevant regulations. To resolve any questions arising from the clinical data management review process, data queries and/or site notifications will be issued by the sponsor. Discrepancy resolution will be documented within the database audit trail.

8.3. Electronic signatures

The PI will electronically sign each individual eCRF after the data has been cleaned, monitored and reviewed. The electronic signature asserts that the investigator reviewed the eCRFs, the data queries, and the site notifications, and agrees with the content. Any changes made to the data after an electronic signature has been applied will result in invalidation of the original signature, and the PI will be required to re-sign the data after reviewing the change(s).

	QMS document Nerivio TCH-008 Clinical Study Protocol	Doc ID: TEC0250 Revision #: 3.0 Page: 48 of 58
---	--	--

8.4. Verification, validation and securing of electronic data capture system

Verification and validation of the EDC and eCRFs will be performed by a team comprising representatives of the developer, the sponsor and at least one of the participating sites. A verification and validation report will be detained by the sponsor.

8.5. Records and data retention

A copy of all records (e.g., informed consent documents, source data, safety reports, study device dispensing records, etc.) which support case report forms for this study, will be retained in the files of the responsible investigator for a minimum of five (5) years following notification by the sponsor that all investigations (not merely the investigator's portion) are completed, terminated and/or discontinued. If the principal investigator retires, relocates, or for other reasons withdraws from the responsibility of keeping the study records, custody must be transferred to a person who will accept the responsibility. The sponsor must be notified in writing of the name and address of the new custodian within 5 days after such transfer occurs.

The database will be retained by the EDC system provider for a minimum of 5 years.

8.6. Other aspects of clinical quality assurance

The site PI or a person designated by the site PI is responsible for establishing and maintaining compliance with the study protocol. The study PI is responsible for addressing quality assurance issues (e.g. correcting procedures that are not in compliance with the protocol). The study coordinator is responsible for quality control issues (e.g. correcting errors in data entry). The sponsor will monitor the investigational sites throughout the study. All outstanding issues and findings that site personnel become aware of will be communicated and handled in agreement with a monitoring plan. An independent DMC will be responsible for providing oversight of the data monitoring issues and conducting periodical reviews that may include recommendations regarding enrollment, continuation, modification, or termination of the study. Site audits by the sponsor may be conducted before the completion of the study to ascertain data quality and integrity.

The Food and Drug Administration (FDA) and/or the local state health authorities may request access to all study records, including source documents, for inspection. The investigator and site staff agree to cooperate with these audits. The investigator must notify the sponsor of any health authority audit as soon as notification of such audit is made. A representative or designee of sponsor may be present during a health authority audit.

	QMS document Nerivio TCH-008 Clinical Study Protocol	Doc ID: TEC0250 Revision #: 3.0 Page: 49 of 58
---	--	--

9. AMENDMENTS AND DEVIATIONS FROM THE PROTOCOL

9.1. Protocol amendments

The protocol cannot be amended by the investigator without obtaining the sponsor's approval. Protocol amendments will be submitted for approval to local IRB/EC and, if applicable, to the respective regulatory authority (RA). The amendments can be implemented in the study only after an IRB/EC and/or RA approval are obtained. Non-substantial changes (e.g. minor logistical or administrative changes, change of monitor(s), telephone numbers, renewal of insurance) which do not affect the rights, safety and well-being of human subjects and/or are not related to the clinical investigation objectives or endpoints, may only require a notification to the IRB/EC and/or regulatory without protocol amendment.

The following documents are relevant to the protocol but are not considered part of the protocol. These documents are stored and modified separately. As such, modifications to these documents do not require protocol amendments:

- Site roster
- Case report forms
- Data management plan
- Monitoring plan
- Statistical analysis plan

9.2. Protocol deviations

A protocol deviation is any noncompliance with the clinical study protocol, Good Clinical Practice, or related SOPs requirements. The deviation may be associated with the subject, the investigator, or study personnel. The investigator/co-investigators must obtain the sponsor's approval for all protocol deviations, except for cases in which the safety and well-being of a patient will be affected, as stated in section 4.5.4 b of the ISO 14155 (2011).

Compliance with the protocol will be assessed by the study monitor during the monitoring visits as well as remotely, using designated reports provided by the EDC system.

All protocol deviations will be addressed in study subject source documents and promptly reported to the site IRB, according to local requirements.

9.3. Procedures for recording, reporting and analysing protocol deviations

All protocol deviations will be documented in source documents and appropriate eCRFs.

The study monitor is responsible for identifying and reviewing protocol deviations with the investigator or designee and documenting the issue and action/outcome of the protocol deviation in the MVR and any follow up letter/communication with the principal investigator.

	QMS document Nerivio TCH-008 Clinical Study Protocol	Doc ID: TEC0250 Revision #: 3.0 Page: 50 of 58
---	--	--

The study monitor will ensure that major protocol deviations are discussed with the investigator. Major deviations include deviations that:

- impact patient safety
- alter the risk/benefit ratio
- compromise the integrity of the data
- affect willingness of the patient's participation in the study

The deviations will be reported to the IRB/EC periodically or as specified by the local regulations. Further documentation of any changes in research activity should be submitted to the sponsor and the IRB/EC if the deviations are related to any instance of serious or continuing non-compliance with governing regulations/requirements of the IRB/EC, and/or related to changes in protocol specified patient activity and procedures.

In addition to the immediate reporting, the study monitor will document all deviations in the monitoring visit report and follow-up letters. The monitor will discuss deviations with relevant site personnel. If needed, a note to file will be issued and filed in the relevant file and a copy will be sent to the sponsor. The sponsor or its designee will review records of deviations and will consider the need for corrective and preventive action and further external reporting to regulatory authorities. Deviations will be summarized and included in the study report. The potential impact/lack of impact of the deviations on the study results will be assessed.

9.4. Notification requirement and timelines

Major deviations should be escalated to the sponsor within 5 business days. Protocol deviations must be reported to local IRB/EC according to their guidelines. The site PI or other designated site staff member is responsible for adhering to local IRB/EC requirements.

10. DEVICE ACCOUNTABILITY

The devices will be provided by Theranica Bioelectronics (sponsor), with all required labeling. The device number will be documented in the CRF and in the site log when provided to the participant. Each batch of devices delivered to the clinical sites for allocation to study participants will be accompanied with a shipment note. The device shipment records will be maintained by the sponsor as well as on site.

Prior to distribution, the devices will be stored in a designated locked cabinet. The access to the investigational devices will be controlled by the research staff. The devices will only be used in the clinical investigation and according to the study protocol.

Each device has a sticker on it with a unique number. When a device will be provided to the participant, it will be paired with the participant's smartphone using Bluetooth

	QMS document Nerivio TCH-008 Clinical Study Protocol	Doc ID: TEC0250 Revision #: 3.0 Page: 51 of 58
---	--	--

connection. During device allocation, application installation and device–smartphone pairing, a site allocated user ID will be entered by the study coordinator via the application. The three IDs (user ID, phone ID, device ID) provide a mean for identifying technical and PRO data from each participant in the electronic database while protecting participant's privacy.

The investigators will be responsible for the safe storage of the devices according to the instructions provided by Theranica Bioelectronics, with restricted access to the investigational materials in their possession, thereby preventing use of any materials by any person not participating in the study. The device accountability records will be reviewed during the monitoring visits.

The investigator will be responsible for providing device use training to the participants according to the instructions for use and protocol and for maintaining product inventory and records. As part of study closure, all unused devices must be returned in their original packaging to Theranica Bio-Electronics.

